8. PRECISION BY SAMPLE SIZE.....	16
9. STUDY LIMITATIONS.....	16
10. STUDY MANAGEMENT.....	17
10.1. Ethical approval and subject consent.....	17
10.2. Subject confidentiality	17
10.3. Reporting of adverse drug events	17
10.4. Study reporting and publications	17
11. APPENDICES	18
11.1. Screener.....	18
11.2. Questionnaire	23
11.3. GlaxoSmithKline Adverse Drug Reaction Form – Revised Nov 30, 2009	40

LIST OF ABBREVIATIONS

AE	Adverse Event
AED	Anti-epileptic drug
DHCP	Dear Healthcare Provider (Letter)
GSK	GlaxoSmithKline
HCP	Healthcare Provider
REMS	Risk Evaluation and Mitigation Strategy
US	United States

Trademark Information

Trademarks of the GlaxoSmithKline group of companies
POTIGA
LAMICTAL
LAMICTAL ODT
LAMICTAL XR
TREXIMET

Trademarks not owned by the GlaxoSmithKline group of companies
None

PROTOCOL SUMMARY

Rationale

As part of a post-marketing commitment, GSK will conduct a survey of prescribers' and pharmacists' understanding of the risk of urinary retention with POTIGA™ products. This is to address the effectiveness of the Risk Evaluation and Mitigation Strategy (REMS) as outlined in the REMS approved by the FDA on 10th June 2011.

Objective(s)

The objectives of this survey are to assess prescribers' and pharmacists' understanding of the risk of urinary retention and the symptoms of acute urinary retention potentially associated with POTIGA use as evaluated by a survey instrument.

Study Design

This is a cross-sectional study of approximately:

1. 200 physicians (e.g. neurologists/epileptologists/neurosurgeons) who have prescribed POTIGA at least once in the last 12 months.
2. 200 pharmacists who have dispensed an anti-epileptic drug (AED) at least once in the last 3 months.

Individuals eligible for the survey will be asked to take the survey online or via a telephone interview if the latter is preferred.

Study Endpoints/Assessments

The primary outcome of the survey is the proportion of physicians and pharmacists providing correct responses to a series of questions concerning the risk of urinary retention and the symptoms of acute urinary retention that may be associated with POTIGA. The risks captured will be those described in the POTIGA Dear Healthcare Provider (DHCP) letters, specifically risks of urinary retention.

1. INTRODUCTION

POTIGA was approved with a FDA requirement for a Risk Evaluation and Mitigation Strategy (REMS). The goal of the REMS for POTIGA is to inform healthcare professionals of the risk of urinary retention and the symptoms of acute urinary retention in patients taking POTIGA. The REMS is comprised of a communication plan for healthcare professionals that is designed to disseminate information about the risk of urinary retention with POTIGA and highlight this potential risk and the need to inform patients to seek immediate medical attention for symptoms of urinary retention, inability to urinate, and/or pain with urination. There are two elements of the communication plan: (1) A Dear Healthcare Professional (HCP) Letter designed to disseminate information about the risk of urinary retention with POTIGA; letters are disseminated within 4 weeks of first retail availability (actual – May 7, 2012) and annually for the next two years (2) a REMS Program Website (available at time of launch; actual -April 16, 2012).

The target audience for these communications is: (1) Prescribing physicians i.e., Epileptologists, Neurologists and Neurosurgeons, (2) Pharmacists dispensing POTIGA tablets and the Medication Guide.

As a condition of approval, FDA requires that GlaxoSmithKline (GSK) assess the effectiveness of the communication plan. Accordingly, a survey will be conducted among a sample of prescribing physicians to evaluate whether they can recall the risk of urinary retention with POTIGA. In addition, the survey will evaluate where HCPs prefer to seek information for POTIGA, for example Dear HCP letters, website, or product labeling. The survey will concentrate on the risks described in the DHCP letter for POTIGA, though it is recognised that the DHCP letter is not the only source of information concerning risks associated with medication use. The design for this study is based on previous experience of risk management programs for GSK products.

A survey will also be conducted among a sample of pharmacists to evaluate whether they can recall the risk of urinary retention with POTIGA.

Although the Marketing Application was approved June 10, 2011, initial retail availability could not commence until after the Drug Enforcement Administration (DEA) had completed rule making placing POTIGA into Schedule V under of the Controlled Substances Act. The drug did not become available to patients until early May 2012 (first distribution to wholesalers April 19, 2012). FDA has agreed that with such delayed retail availability of POTIGA, an assessment of HCP understanding submitted on June 10, 2012 would provide little meaningful information. Therefore, the first assessment of the REMS survey will be included with the report due on June 10, 2013.

Originally, ER physicians and urologists were planned to be included in the survey as well. Given the survey will target prescribers only, as of FDA feedback received on January 25, 2013, ER physicians and urologists will no longer be targeted in the survey.

POTIGA was generally available to prescribers and patients for the first time in May 2012 and to date, there has been modest prescribing of the product. The impact of this on

the recruitment goals is uncertain but represents a potential challenge for GSK in this first assessment of HCP knowledge.

2. OBJECTIVE(S)

The objectives of this study are:

1. To assess prescribers' understanding of the risk of urinary retention and the symptoms of acute urinary retention with POTIGA as evaluated by a survey instrument.
2. To assess pharmacists' understanding of the risk of urinary retention and the symptoms of acute urinary retention with POTIGA as evaluated by a survey instrument.

3. INVESTIGATION PLAN

3.1. Study Design

This study is sponsored by GlaxoSmithKline (GSK), and will be conducted by Concentrics Research LLC, a contract research organization, on behalf of GSK.

This is a cross-sectional study of individuals prescribing POTIGA or dispensing AEDs.

Physicians and pharmacists will be recruited using a multi-modal approach:

1. Telephone
2. Email
3. Fax

Screening interviews will take place via telephone, email or fax using a standardized screening questionnaire to assess whether the physician or pharmacist is eligible for and interested in participating in the study. Also, demographic information including clinical specialty and geographic location will be collected at screening.

Following recruitment, physicians' and pharmacists' understanding of the risk of urinary retention and the symptoms of acute urinary retention with POTIGA products will be evaluated using an online survey or the same survey instrument delivered during a telephone interview. If the healthcare provider (HCP) qualifies and is interested in participating, the survey recruiter will schedule an appointment for the interview if the HCP states a preference for the telephone survey, or will send an email including a link to the online survey with their unique passcode. The telephone option will be made available to accommodate individuals who would prefer a telephone call to participate in the survey. It is estimated that approximately 85% will complete the internet survey and the remaining 15% will complete the survey via telephone interview. HCPs will be allowed to respond throughout the entire data collection period, and non-responders will receive up to 5 follow-up messages (sent either via email or phone call) to remind them to participate in the survey.

All physicians and pharmacists will be asked to re-confirm their clinical specialty at the start of the interview (whether online or via telephone). Prescribing physicians (e.g. neurologists, neurosurgeons, epileptologists) will be asked medications prescribed again as well, and pharmacists will similarly be asked to confirm medications dispensed again. Any prescribing physician or pharmacist will be excluded from the survey if he/she gives an answer to these screening questions that would be inconsistent with an answer provided previously during the telephone screening and would also meet an exclusion criteria.

To ensure consistency across interviews, all HCP assessments will be conducted in a structured manner, where all interviews (telephone and on-line) follow a standardized script, and both telephone and on-line surveys will provide the same response options for each question for each participant. Telephone interviewers will be trained on the protocol and questionnaire, as well as following general interviewing practice and quality standards. Telephone interviewers will not be allowed to deviate from the survey procedure or supply additional information or instructions.

Prior to start of the survey, HCPs will be asked to electronically sign a Confidentiality and Consent Agreement, which describes the purpose of the study, data handling, storage and security, expectations of confidentiality of study data and participation, honoraria for study participation, and their rights as a survey subject. All HCPs completing the survey will be required to confirm that he/she is the same HCP who was screened previously to help safeguard against delegation of participation to other colleagues or staff in the HCP's office/pharmacy. Following the HCP's agreement with the Confidentiality and Consent form, the interviewer will administer the telephone survey or the internet survey will begin.

Prior to implementation of the full survey, a pilot study will be conducted involving 30 healthcare providers (HCPs) (10 prescribing physicians, 5 urologists, 5 emergency room physicians and 10 pharmacists), enrolled to complete the survey via telephone. Approximately 5 of the prescribing physicians included in the pilot will have prescribed POTIGA. The objectives of the pilot are to test the physicians' and pharmacists' understanding of the draft questions and follow-up responses, in order to understand the nature of the responses and why specific responses were selected. Feedback from HCPs is intended to improve the clarity of the survey questions and answers. Following the completion of the pilot, all study implementation procedures and assumptions will be reviewed to determine if changes in study procedures and/or training of survey administrators will be required prior to implementation of the full survey.

3.2. Study Population

A listing of physicians eligible to complete the survey will be compiled at one research center utilizing a custom database of approximately 500,000 geographically and therapeutically diverse physicians from all 50 states. Working with a partner, this research center also has access to over 168,000 geographically diverse pharmacists from all 50 states.

Pharmacists and physicians in the targeted specialties will be contacted initially via multiple methods, including, telephone, e-mail, and/or fax, with an invitation to participate in the study. Interested physicians will be asked to contact the market research center staff on the study, who will then complete a telephone screening process to determine if the physician meets all of the study protocol-defined eligibility criteria (see Section 4.2.1 and Section 4.2.2) and, to confirm their interest in participating in the survey if they do meet the eligibility criteria. Eligible physicians who agree to participate will be scheduled for either an appointment with an interviewer to complete the survey via telephone or they will be provided an email containing a link to an on-line survey for completion along with their unique access passcode.

For prescribing physicians, the honorarium for completing the survey will be \$125, and for pharmacists, the honorarium will be \$50. The honorarium for the prescribing physicians was increased from \$100 to \$125 after the start of the study, due to recruitment being significantly lower than expected.

3.3. Discussion of Design

The final study design is based on experience from risk management studies previously completed by GSK.

3.3.1. Risk management studies for other GSK medications

Experience from previous risk management studies was used to determine the threshold for the proportion of correct responses per individual survey question against which to base sample size calculations and precision estimates.

The REMS post marketing commitments for LAMICTAL™ (NDA 022115) included:

- a. A survey of patients' understanding of the serious risks of Lamictal (lamotrigine) Orally Disintegrating Tablets
- b. A report on periodic assessments of the distribution and dispensing of the Medication Guide in accordance with 21 CFR 208.24
- c. A report on failures to adhere to distribution and dispensing requirements, and corrective actions taken to address noncompliance

The REMS post marketing commitments for TREXIMET™ (NDA 21-926) included:

- a. Survey of patients' understanding of the serious risks of TREXIMET;
- b. Report on periodic assessments of the distribution and dispensing of the Medication Guide in accordance with 21 CFR 208.24; and,
- c. Report on failures to adhere to distribution and dispensing requirements, and corrective actions taken to address non-compliance.

Based on these studies, a threshold of 80% was determined to be acceptable for the proportion of subjects answering correctly the questions regarding risks associated with POTIGA. This threshold will be imposed for prescribers and pharmacists, not urologists

nor emergency room doctors. Prescribers and pharmacists are the HCPs who will play an important role in re-enforcing the safety messages for POTIGA.

It should be noted that TREXIMET and POTIGA REMS have since been revised, because the FDA determined that a Medication Guide is not necessary to ensure the benefits of the drug outweigh the risks described above because labeling and a REMS that includes a communication plan will be adequate to describe these serious risks. The Medication Guide will be part of the approved labeling and be subject to the requirements under 21 CFR 208.

4. SUBJECT SELECTION AND ELIGIBILITY

4.1. Number of Subjects

This survey aims to recruit approximately 400 total POTIGA prescribers and pharmacists. These numbers reflect a trade-off between what is practical in terms of recruitment, given the relatively low predicted uptake of POTIGA, and providing sufficient precision around outcome estimates (proportion giving correct responses per question) (Section 8).

Ideally, this study aims to recruit a sample of physicians and pharmacists from a demographically representative population database who prescribe POTIGA (neurologists, neurosurgeons, epileptologists), and dispense POTIGA (pharmacists). In order to achieve 400 completed interviews, it is anticipated that approximately 4,000 potential physicians or pharmacists may be contacted for potential recruitment for this study.

4.2. Inclusion and Exclusion criteria

4.2.1. Inclusion criteria

Physicians and pharmacists will be required to meet all the following inclusion criteria:

1. Able to read, speak, and understand English.
2. Willing to take the online survey or have the survey administered via a telephone interview, including electronically signing a Confidentiality & Consent agreement and completing all study protocol-specified procedures.
3. Prescribing physicians and pharmacists:
 - a. Practicing physician or pharmacist who sees and treats, or fills prescriptions for, patients with epilepsy, currently (within the past 12 months).
 - b. Prescribed POTIGA within the past 12 months (prescribing physicians)
 - c. Filled a prescription for at least one AED within the previous three months (pharmacists).

4.2.2. Exclusion criteria

Physicians or pharmacists meeting any of the following criteria will not be eligible to take the survey:

- a. The physician or pharmacist is currently employed by, or is a representative of any of the following:
 - A A pharmaceutical company or manufacturer of medicines or healthcare products.
 - B Contributor/editor to published guideline committees for epilepsy or UR.
- b. The physician or pharmacist has a visual impairment that would prevent him or her from being able to read independently.
- c. The physician or pharmacist participated in the Pilot REMS study for POTIGA.
- d. The physician or pharmacist is an employee of GSK or Concentrics Research.

5. STUDY ASSESSMENTS AND PROCEDURES

5.1. Screening and baseline assessments

Subjects participating in the pilot study will be removed programmatically from the sample list in order to avoid bias in the screener by specifically mentioning the drug name, even in a masked approach, during screening which may heighten awareness prior to the interview.

After accepting the initial recruitment invitation to participate in the study, individuals will be scheduled for a telephone screening interview. The screener will assess:

- Inclusion/exclusion criteria
 - The screener was amended after the study began to ask physicians a subset of epilepsy drugs at Q7 instead of the full list previously included. This subset still allows for masking of the drug to be studied (POTIGA), but shortens the burden on the physician to respond to the full listing during recruitment. This revision was made based on qualitative feedback during recruitment where physicians were not continuing with screening due to frustration with the length of this question. After reviewing data gathered to date, the most common responses to the drugs prescribed were included in the remaining listing, along with POTIGA.
 - Whether POTIGA has been prescribed within the past 12 months (physicians) or whether AEDs have been dispensed within the past 3 months (pharmacists).
 - Demographics: geographic region and type of healthcare provider. Additional prescribing or dispensing-related questions will be asked in the main survey questionnaire.

5.2. Outcomes

Subject understanding of the risk of urinary retention and the symptoms of acute urinary retention associated with POTIGA will be assessed using the survey instrument.

The primary outcome of this study is the proportion of subjects that correctly respond to individual survey questions concerning the risk of urinary retention and the symptoms of acute urinary retention associated with POTIGA. The order in which potential responses to survey questions appear will be randomized. The proportion responding correctly will be tabulated separately for each item in the subject understanding survey instrument. These risks represent those described in the DHCP letter.

At the conclusion of the online survey, the final screen will display a summary of the relevant information from the POTIGA prescribing information, and a link to <http://www.potiga.com>. The phone respondents will be offered materials by email or the POTIGA website, but will also be given the toll-free number for the POTIGA response center [name] ([name]).

5.3. Adverse drug experience/event measures

This study will not investigate adverse events associated with the use of POTIGA. Whilst it is not the intention of the survey to solicit adverse events (AEs), it is possible that a respondent may spontaneously provide information that meets the criteria of an adverse event. Any reported adverse events will be entered into the GSK Safety Database:

- Online respondents will be provided with the number for the GSK Global Clinical Safety and Pharmacovigilance Response Center at the end of the online survey and will be directed to call the Center to report any adverse events potentially associated with POTIGA.
- If, at any time during the telephone interview, the subject describes an adverse event associated with POTIGA or any GSK product, the interviewer will complete an adverse event form and fax it to GSK Global Clinical Safety and Pharmacovigilance at [contact] within 24 hours of receiving the information.

At the end of the project, Concentrics shall provide a summary of all AEs that it has submitted to GSK to enable the reports to be reconciled.

6. DATA COLLECTION AND MANAGEMENT

Subject data from the screening and survey response parts of the questionnaire will be stored confidentially in password protected systems maintained by Concentrics Research.

In all cases, subject identifiers will not be collected or transmitted to GSK according to GSK policy. All subjects will be given a numeric subject identifier.

7. DATA ANALYSIS

7.1. Analysis Populations

The population for analysis will comprise all physicians and pharmacists recruited into the study, meeting eligibility criteria as assessed in the survey screener, and completing the survey.

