ALLOW MULTIPLE RESPONSES, EXCEPT PUNCH 6 OR 7.

Patients with benign prostatic hyperplasia (BPH)	1
Patients who are unable to communicate clinical symptoms (e.g. cognitively impaired patients)	2
Patients who use concomitant medications that may affect voiding (e.g. anti-cholinergics)	3
Patients who use non-steroidal anti-inflammatory drugs (NSAIDs)	4
Patients who are obese	5
None of the above	6
I don't know	7

SHOW SECTION B ONLY IF ANY RESPONSES (Q1-13) WERE INCORRECT

SECTION B: For the next set of questions, I'd like to ask you to provide some further information on some of your responses. Please provide as much detail of your thought process as possible when responding.

SHOW Q1_1 THROUGH Q13_1 ONLY FOR ANY INCORRECT RESPONSES AT Q1-13. THESE ARE OPTIONAL QUESTIONS. SHOW QUESTION TEXT FOR EACH, THEN THE QUESTION (1_1 – 13_1).

1_1) Previously, at Question 1, you responded [INSERT Q1 RESPONSE]. What led you to choose that response?

2_1) Previously, at Question 2, you responded [INSERT Q2 RESPONSE]. What led you to choose that response?

3_1) Previously, at Question 3, you responded [INSERT Q3 RESPONSE]. What led you to choose that response?

4_1) Previously, at Question 4, you responded [INSERT Q4 RESPONSE]. What led you to choose that response?

5_1) Previously, at Question 5, you responded [INSERT Q4 RESPONSE]. What led you to choose that response?

6_1) Previously, at Question 6, you responded [INSERT Q6 RESPONSE]. What led you to choose that response?

7_1) Previously, at Question 7, you responded [INSERT Q7 RESPONSE]. What led you to choose that response?

8_1) Previously, at Question 8, you responded [INSERT Q8 RESPONSE]. What led you to choose that response?

9_1) Previously, at Question 9, you responded [INSERT Q9 RESPONSE]. What led you to choose that response?

10_1) Previously, at Question 10, you responded [INSERT Q10 RESPONSE]. What led you to choose that response?

11_1) Previously, at Question 11, you responded [INSERT Q11 RESPONSE]. What led you to choose that response?

12_1) Previously, at Question 12, you responded [INSERT Q12 RESPONSE]. What led you to choose that response?

13_1) Previously, at Question 13, you responded [INSERT Q13 RESPONSE]. What led you to choose that response?

SKIP TO DEMOGRAPHICS (B) IF QA = PUNCH 4 OR 5. CONTINUE TO DEMOGRAPHICS (A) IF QA = PUNCH 1, 2 OR 3.

DEMOGRAPHICS (A)

The next sets of questions are about your practice history so that we can group your responses with others like you.

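### Analysing only survey completers, when extra questions are shown only after wrong answers, can bias the percent correct upwards

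*Protocol*

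**What the plan says.** Section 7.1 defines a single analysis population: "all physicians and pharmacists recruited into the study, meeting eligibility criteria as assessed in the survey screener, and completing the survey". The protocol neither defines completion nor says what happens to partial records.

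Section 7.2 makes the primary outcome the proportion correct on each question and sets 80% per question as the mark of sufficient understanding, for prescribers and pharmacists alike.

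The order of the questionnaire in Section 11.2 matters here:

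- Q1 to Q13 are the knowledge items.
- Section B follows, with the routing instruction "SHOW SECTION B ONLY IF ANY RESPONSES (Q1-13) WERE INCORRECT". Its probes are governed by "SHOW Q1_1 THROUGH Q13_1 ONLY FOR ANY INCORRECT RESPONSES AT Q1-13", so there is one per wrong answer and at most 13. Respondents are asked: "Please provide as much detail of your thought process as possible when responding". The same instruction adds "THESE ARE OPTIONAL QUESTIONS".
- Demographics come next (the routing line after the last probe begins "SKIP TO DEMOGRAPHICS (B) IF QA = PUNCH 4 OR 5"), then Section C (Q29 and Q30) and the closing text.

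Section 3.2 ties the honorarium (125 USD for physicians, 50 USD for pharmacists) to completing the survey.

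**The concern.** By the end of Q13 everything needed for the primary outcome has been recorded. What remains before completion is longer for a respondent with more wrong answers, because each one adds a free-text screen. If that extra load makes people stop, those who stop are disproportionately the ones with wrong answers, and 7.1 then removes them from the denominator. The completers would look better informed than the respondents who actually answered the items.

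The stake is the comparison with 80%. The margin of error in Section 8 covers sampling variation only, and a larger sample would not remove this bias. Section 9 does not list it among the limitations.

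Two features make the mechanism plausible. Section 5.1 records that physicians abandoned the screener because one question was too long, and that the question was shortened for this reason. Pharmacists qualify by dispensing any anti-epileptic drug (Section 4.2.1), so some may know little about POTIGA and meet many probes, and theirs is the smaller honorarium.

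**Working it through.** **The plan's own precision figure.** Section 8 gives ±5.5 points for n = 200 and 80% correct. The half-width is 1.96 × √(0.80 × 0.20 / 200) = 0.0554, or 5.5 points, so it reproduces. It is the yardstick for the bias below.

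**Bias formula for one item.** Let p be the true proportion correct among those who answered, d0 the break-off after Q13 among responders correct on that item, and d1 the break-off among those incorrect. Among completers

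p_obs = p(1 − d0) / [p(1 − d0) + (1 − p)(1 − d1)].

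The protocol gives neither d0 nor d1; every value here is an assumption. Only the ratio (1 − d1)/(1 − d0) matters, so d0 = d1 gives no bias.

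**Results with d0 = 0.**

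| d1 | true 75% reads | true 80% reads |
|---|---|---|
| 0% | 75.0% | 80.0% |
| 5% | 75.9% | 80.8% |
| 10% | 76.9% | 81.6% |
| 20% | 78.9% | 83.3% |
| 30% | 81.1% | 85.1% |

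Example: 0.75 / (0.75 + 0.25 × 0.90) = 0.75 / 0.975 = 76.9%.

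**Results with some break-off in both groups, true 75%.**

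- 2% and 10%: 0.735 / (0.735 + 0.225) = 76.6%.
- 5% and 20%: 0.7125 / (0.7125 + 0.200) = 78.1%.
- 5% and 30%: 0.7125 / (0.7125 + 0.175) = 80.3%.

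**Break-off needed to reach 80%.** Setting p_obs = 0.80 with d0 = 0 gives d1 = 1 − 0.25p/(1 − p). That is 6% from a true 79%, 11% from 78%, 16% from 77%, 25% from 75% and 42% from 70%.

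**Check across 13 items.** The one-item formula takes d0 and d1 as given, although people correct on one item still meet probes for others. A simulation of 500,000 respondents used 13 items at a true 75% each, a constant chance h of stopping at each probe, and a within-respondent correlation rho between items. The bias in points was:

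| rho | see at least one probe | h = 1% | h = 2% | h = 5% | h = 10% |
|---|---|---|---|---|---|
| 0 | 98% | +0.2 | +0.4 | +0.9 | +1.9 |
| 0.2 | 81% | +0.6 | +1.3 | +3.1 | +5.9 |
| 0.4 | 65% | +1.1 | +2.1 | +5.1 | +9.2 |

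Most respondents would see some probes; what differs is how many. The cells at or above about 5 points are those where 14% to 26% of all respondents stop after Q13 (completers 86%, 76% and 74%).

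**The case against.** The strongest reply is that nothing in the protocol shows differential break-off. The probes can be skipped, the honorarium is for completing, and about 15% are expected to be interviewed by telephone (Section 3.1). The abandonment noted in Section 5.1 happened in the screener, where the honorarium is mentioned only at the end. All of this stands, and it makes the larger scenarios less likely. It does not remove the mechanism, because the extra screens still appear only after wrong answers.

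Second, the link to the outcome is diluted. Seven of the 13 items (Q1, Q2, Q4, Q5, Q6, Q9 and Q10) concern indication, monotherapy, dose, age or food rather than urinary retention, yet errors on them also trigger probes. This stands as a reason to expect a smaller effect on the retention items.

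Third, completion is undefined. Section 11.2 lists the assessment survey and the demographic profile as separate parts, so someone who stops in demographics might still count as complete, and an analysis plan could settle this. That is fair, but Section B comes before demographics. If completion is meant to be reached at Q13, the problem disappears and 7.1 need only say so.

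Fourth, Section 10.1 treats consent as implied by completing the survey, which might seem to bar the use of partial records. Section 3.1, however, requires an electronically signed agreement before the survey starts. The two passages need aligning, but the objection does not block the fix.

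Finally, the study is descriptive and a bias of 1 to 2 points is well inside ±5.5. True, but 7.2 still applies the 80% threshold, and the confidence interval does not cover this bias.

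**Conclusion.** The point holds as a weakness in design. The completer rule, combined with Section B placed before the end, lets exclusion depend on the primary outcome, and bias by this route would run towards the threshold. Its size is unknown: zero with equal or no break-off, about 1 to 2 points for a true 75% if 5% to 10% of incorrect responders and no correct ones stop, and enough to carry a true 75% to 80% only at about 25%. For an item already close to the threshold, less is needed (6% from a true 79%).

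A reader might infer that the reported percentages are inflated, or that failing items will pass. The documents do not support that. They contain no break-off data, and the step from 75% to 80.3% needs the most extreme pair tried with break-off in both groups, six times as high among incorrect as among correct responders.

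**What to change.** In Section 7.1, define the primary analysis set as all eligible respondents who signed the Confidentiality and Consent Agreement and answered the knowledge items, whether or not they finished Section B, demographics or Section C. Respondents who stopped before Q13 should count in the denominator of each item they answered. Break-off at Section B then has no effect on the estimates.

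Report break-off after Q13 by number of wrong answers, counted as the routing counts them. The protocol does not say whether a don't-know answer triggers a probe, so this should be stated. Give the completers-only result as a sensitivity analysis. Align the implied-consent wording in 10.1 with the signed agreement in 3.1.

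The cost is small: a revised sentence in 7.1, one extra table, and retention of partial records, which the protocol does not confirm are kept. Demographics will be missing for some partial responders, so the subgroup tables will have smaller denominators than the overall results.

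Moving Section B after Section C is optional and largely redundant once the analysis set changes. Sections 3.2 and 5.1 describe changes made after the study began, so re-routing now could create two versions of the instrument. It is better left to a later survey wave.
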